10.6 Other Parameters for Evaluation of Treatment Effect

10.6.1 Quantification of *O. formigenes*

The possibility to monitor the natural occurrence of *O. formigenes* bacteria and the presence of the *O. formigenes* drug before, during and after treatment with OC5 is an important tool for control of the pharmacodynamics of the drug. To date, two different genotypes of naturally occurring *Oxalobacter formigenes* have been identified, genotype 1 and 2 (groups I and II). Oxabact, or OC5, is of the strain HC-1 of the *O. formigenes* genotype 1. A real-time quantitative PCR assay will be used that permits determination of the numbers of both *O. formigenes* genotype 1 and genotype 2 in faecal samples.

Faecal samples will be collected at the subject's home and shipped to central laboratory MVZ Institut für Mikroökologie GmbH, Herborn, Germany.

A positive treatment effect on the result from analysis of number of *O. formigenes* should show an increased number of *O. formigenes* genotype 1 during treatment period. Earlier studies have shown that *O. formigenes* genotype 2 have increased in the OC5 treated group, but not in the placebo group indicating a transfer of oxalate from plasma to the intestine mediated by OC5 treatment. *O. formigenes* genotype 2 will also be monitored for this reason.

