12.8 Subgroup Analysis

The results of the study will be presented primarily with descriptive individual data graphically presented over time and therefore no additional subgroup analyses will be needed for these. For summaries and/or any other analyses presented the following subgroups will be considered, only if there is sufficient sample size and for the following endpoints: eGFR, total and free plasma oxalate concentration, 24-hour urinary oxalate excretion, stone events, absolute count of *O. formigenes* per gram in stool, speckle tracking and traditional echocardiography). The subgroups are:

- Subjects with a baseline 24-hour urinary oxalate excretion above and equal to or below 1.87 mmol/L/24h/1.73 m² respectively (mean of the two values during screening/baseline of the ePHex study).
- Subjects above or equal to and below 18 years of age at baseline of the ePHex study.
- Subjects with a baseline eGFR above or equal to and below 60 ml/min/1.73m² respectively (mean of the obtained values during screening/baseline calculated by the creatinine based "Bedside Schwartz" equation (2009) for children below 18 years of age and the creatinine based CKD-EPI equation (2009) for adults).
- Race.
- Gender.
- Progressors and non-progressors based on historic eGFR (i.e. eGFR prior to treatment start in the ePHex study).
- Type of PH

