6.3 Other endpoint(s)

In addition, a set of other endpoints are specified, which are considered supportive to the primary and key secondary endpoints:

- Change from baseline in myocardial function as measured by Speckle Tracking and traditional echocardiography.
- Change from baseline in free plasma oxalate concentration.
- Change from baseline in urinary oxalate excretion.
- Grade of nephrocalcinosis as assessed by Ultrasound.
- Change in number of *O. formigenes* in stool.
- Association between change in number of *O. formigenes* in stool and change in total plasma oxalate concentration.
- Change from baseline in score of Quality of Life questionnaire.
- Change from baseline after 12 and 24 months of open-label treatment in markers for renal function, renal tubular capacity and inflammation
 - Urine: magnesium, phosphorus, citrate, calcium, glycolate, creatinine, urea, calcium oxalate crystals, pH, osmolality and urinary volume.
 - Blood: magnesium, phosphorus, citrate, calcium, BUN, ALP, bicarbonate, CRP, WBC, creatinine and Cystatin-C.

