Raw data (in listings) will be presented in the same precision as received. Appropriate rounding will be performed for the following summary statistics: arithmetic mean, LS mean, median, Q1 and Q3, SD (standard deviation), SE (standard error) and two-sided 95% confidence limits will be presented with at least one more decimal than the original data; minimum and maximum values will be presented with the same precision as the original data. In special cases, e.g. after conversion of data, the number of decimals will be determined based on relevance. In frequency tables, percentages will be presented with 1 decimal (except for 100%, if that is the maximum value), unless otherwise stated. P-values will be presented with 3 decimals, and those smaller than 0.001 will be replaced by <0.001.

Descriptive statistics presented in general summary tables will be the number of non-missing observations (n), arithmetic mean, SD, SE, median, Q1, Q3, minimum and maximum for quantitative data. For qualitative data, frequency counts and percentages will be determined. The

¹ <https://www.fda.gov/files/drugs/published/Submission-of-Abbreviated-Reports-and-Synopses-in-Support-of-Marketing-Applications.pdf>

denominator used when calculating percentages will be the number of subjects in the applicable analysis population. Statistical output will present LS means, SE and two-sided 95% confidence limits, where applicable. All plots will be created using scheduled protocol time or visit on the x-axis. Mean plots will be presenting mean +/- SE.

Baseline is generally defined as the last non-missing planned and valid measurement/assessment before first dose of study drug, unless otherwise specified. Unscheduled measurements are excluded as baseline value, unless otherwise specified. Change from baseline is calculated as the value at a specific time point minus the value at baseline. For this study, the following definitions are used to define the baseline measurement:

- The first baseline is defined as the baseline of the ePHex study, which is specified per ePHex SAP for each of the assessments.

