grade 0: no echogenicity

grade 1: mild echogenicity around medullary pyramid borders

grade 2: moderate echogenicity around and inside pyramids

grade 3: severe echogenicity of entire pyramids

Grades and shifts will be summarized for left and right kidney separately. In addition, shifts will be classified (and presented) following the addendum referred to in section 11.1. Shift tables will be presented as a crosstabulation comparing baseline and 12/24 months values.

Stool

Data collected for *O.formigenes* in stool (as genotype 1 and genotype 2) will only have measurable values if above the Limit of Detection (LOD). Values below the LOD will be replaced for calculation purposes in descriptive statistics, plots and statistical analyses (see section 11.1). The proposed analyses will only be performed if there is a limited amount (<15%) of data below LOD present on-treatment. The values will be presented as '< LOD' in the listings.

Note that in case of a provided actual value lower than the LOD, it will be presented and used as is and not imputed.

Based on previous studies, it is expected that the number of subjects positive for genotype 2 at screening/baseline and throughout the study will be very low. Therefore, in case genotype 1 or 2 is not detectable in the majority of data (see above), the analysis for that genotype will not be performed and data for that genotype will then be limited to a listing. All descriptive statistics and plots will be done separately on number of *O. formigenes* genotype 1 and 2 respectively, if applicable.

Descriptive statistics will be used to present the observed and change from baseline values per treatment group and overall over time, using two baselines. Change in number of *O. formigenes* stool will be based on number of *O. formigenes* at month 24 compared to baseline in the O - O group versus the P - O group. The measurement at month 12 will be used as supportive data.

Analyses on the total number of *O. formigenes* (i.e. the sum of genotype 1 and genotype 2) may be done as post-hoc analyses, and this depends upon the number of values <LOD.

Quality of Life questionnaires

Quality of life scoring is assessed with the questionnaires SF36V2 (for adults ≥ 18 years) or CHQ/PF50 (for children ≥ 5 years). For children younger than 5 years of age, it is likely that no information from the questionnaire is available, and data will remain missing.

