14.2.43	Spaghetti plots per treatment group of the actual free plasma oxalate values (FAS)
14.2.44	Descriptive statistics urinary oxalate excretion (FAS) – raw and cfb - both centrifuged and non-centrifuged urinary oxalate
14.2.45	Descriptive statistics urinary oxalate excretion by subgroup (FAS) – raw and cfb - only non-centrifuged urinary oxalate
14.2.46	Descriptive statistics grade of nephrocalcinosis (FAS), left and right kidney separately. Including shifts classifications, unilateral and bilateral
14.2.47	Descriptive statistics O.formigenes - (FAS) – raw and cfb
14.2.48	Descriptive statistics O.formigenes by subgroup (FAS)
14.2.49	Descriptive statistics QoL SF36V2 (FAS) – raw and cfb
14.2.50	Descriptive statistics QoL CHQ/PF50 (FAS) – raw and cfb
14.2.51	Renal markers urine including excretion values (FAS) – raw and cfb
14.2.52	Renal markers blood (FAS) – raw and cfb
14.3 Safety Data Summary figures and tables – 14.3.1 Displays of Adverse Events	
14.3.1.1	Overview of treatment emergent events
14.3.1.2	Treatment emergent adverse events, by SOC and PT
14.3.1.3	Treatment emergent adverse events by SOC, PT and grade
14.3.1.4	Related treatment emergent adverse events by SOC and PT
14.3.1.5	Related treatment emergent adverse events by SOC, PT and grade
14.3.1.6	Treatment emergent adverse events leading to premature treatment/study discontinuation, by SOC and PT
14.3.1.7	Serious treatment emergent AEs, by SOC and PT
14.3.1.8	Serious and related treatment emergent AEs, by SOC and PT

14.3 Safety Data Summary figures and tables – 14.3.2 Listings of Deaths, Other Serious and Significant Adverse Events	
14.3.2.1	Serious Adverse events
14.3.2.2	Deaths
14.3 Safety Data Summary figures and tables – 14.3.4 Abnormal Laboratory Value Listing (each subject)	
14.3.4.1	Out of range clinical laboratory
14.3.4.2-14.3.4.4	Clinical laboratory (raw and change from baseline) – haematology, clinical chemistry, urinalysis
14.3.5	Vital signs - raw and change from baseline
14.3.6	Physical Examination
14.3.7	Concomitant medication

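### The SAP states no log10 scale or geometric mean for stool O. formigenes counts, so the mean, SE and mean change can be dominated by one subject; the planned medians limit this. The plasma oxalate association has no listed output.

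*SAP*

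**What the plan says.** Protocol 10.6.1 describes the assay: "A real-time quantitative PCR assay will be used that permits determination of the numbers of both" genotypes. Protocol 12.8 names the variable as "absolute count of *O. formigenes* per gram in stool".

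SAP 7.6.3 (Stool) plans the summary: "Descriptive statistics will be used to present the observed and change from baseline values per treatment group and overall over time, using two baselines". It bases the endpoint on month 24 against baseline, with O-O set against P-O and month 12 as support. Values below the detection limit are replaced by a rule held in the programming addendum (SAP 11.1). The analyses run only if fewer than 15% of on-treatment values are below that limit.

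The statistics come from SAP 7.1: "arithmetic mean, SD, SE, median, Q1, Q3, minimum and maximum for quantitative data". The same section defines change: "Change from baseline is calculated as the value at a specific time point minus the value at baseline". SAP 12.3 lists the output as "Descriptive statistics O.formigenes - (FAS) – raw and cfb", plus a subgroup table. SAP 12.4 lists individual counts.

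SAP 6.3 also has an endpoint linking the change in number of O. formigenes "in stool and change in total plasma oxalate concentration". Protocol 12.7 would evaluate this association graphically and gives no axis scale. SAP 7.6.3 gives no method for it, and SAP 12.3 lists no such figure.

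**The concern.** A bacterial count per gram usually varies by factors rather than by fixed amounts. When values differ by orders of magnitude, the arithmetic mean of a small group is close to its largest value divided by the group size, and the SE is driven by the same value. A simple difference from an undetectable or very low baseline is essentially the on-treatment count, so mean change inherits the problem.

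The SAP attends to distribution elsewhere. The eGFR model has a conditional log transformation (SAP 7.6.1), and stone counts have an overdispersion rule (SAP 7.6.2). Nothing comparable is stated for stool.

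Protocol 10.6.1 treats stool monitoring as the pharmacodynamic check on the product. Protocol 4.4.1.6 used an earlier relation between stool number and plasma oxalate to support enteric elimination. At stake is whether the reported mean colonisation, and any display against oxalate, describes the group or one or two people.

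**Working it through.** **Plan figures.** The documents give no mean, spread or power for stool counts, so there is no stool figure to reproduce. The power table in Protocol 12.2 concerns eGFR only. The completer numbers do reproduce: 16 × 0.75 = 12 and 16 × 0.75² = 9. With the 18 subjects reported in SAP 2.4, 18 × 0.75² = 10.1. That is about 8 or 9 per group at entry and 4 or 5 per group at month 24 if the groups are balanced.

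**Assumption.** On-treatment counts are log-normal between subjects, with log10 SD *s*. The documents do not give *s*. I use 0.75, 1.0 and 1.5 as the main range.

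**Share of the largest subject.** For each of 400,000 simulated groups of size *n*, share = max(x) / Σx, where x = 10^(s·Z) and Z is standard normal. The overall level cancels. Median share:

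| log10 SD | n = 8 | n = 5 |
|---|---|---|
| 0.75 | 49% | 58% |
| 1.0 | 59% | 68% |
| 1.5 | 74% | 81% |

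At *s* = 0.5 the figures are 37% and 47%, so the effect is much weaker if counts are less dispersed. At *n* = 8 the chance that one subject holds more than half the total is 20% at *s* = 0.5, 65% at 1.0 and 83% at 1.5.

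**Sensitivity of each summary.** Typical factor by which the statistic changes when the top subject is dropped:

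| n, log10 SD | Arithmetic mean | Geometric mean | Median |
|---|---|---|---|
| 8, 1.0 | 2.1 | 1.6 | 1.3 |
| 8, 1.5 | 3.4 | 2.0 | 1.6 |
| 5, 1.0 | 2.5 | 1.9 | 1.4 |
| 5, 1.5 | 4.3 | 2.6 | 1.6 |
| 4, 1.0 | 2.7 | 2.1 | 2.0 |
| 4, 1.5 | 5.1 | 3.0 | 3.0 |

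The median, already planned, is the most resistant at 5 and 8 per group and loses that advantage at 4. The geometric mean always moves less than the arithmetic mean.

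**Hand example** (invented values): 10⁵, 10⁶, 10⁶, 10⁷, 10⁷, 10⁷, 10⁸, 10⁹. The sum is 1.132 × 10⁹, so the largest value supplies 10⁹ / 1.132 × 10⁹ = 88%. Dropping it moves the arithmetic mean from 1.42 × 10⁸ to 1.89 × 10⁷ (7.5-fold) and the geometric mean from 7.5 × 10⁶ to 3.7 × 10⁶ (2.0-fold). The median stays at 10⁷.

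**Association display.** With 9 subjects, the most extreme point's typical share of the x-axis sum of squares is 0.76 at *s* = 1.0 and 0.84 at *s* = 1.5 on the raw scale, against 0.38 on log10. This shows what the choice of axis would do; the documents do not choose one.

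**Detection-limit substitution.** If a fraction *f* of subjects have an undetectable baseline and the substitute value is halved, the group's geometric mean fold change is multiplied by 2^f: 1.41 at *f* = 0.5 and 2 at *f* = 1. A simple difference for such a subject shifts only by half the substitute value.

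**The case against.** The strongest reply is that the plan already holds the remedy. Median, quartiles and range are summarised, every count is listed, and the median resists one high subject better than a geometric mean at 5 and 8 per group. That stands. A reader might infer that one subject decides the whole group result; the documents do not support that. Only the mean, SD, SE and mean change are exposed.

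A reader might also infer that the plot against plasma oxalate is spoiled by a raw axis. That is not supported either: the SAP lists no such plot, and the protocol fixes no scale. The documented gap is the missing specification.

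Three further points stand in part. The label on the stool table is generic: the SAP uses it for other outputs too, including quality-of-life scores that are presented as T-scores, so it proves nothing about scale. The programming addendum is not available and may set a log scale, but the visible rule is value minus baseline, and the stool text cites the addendum only for detection-limit replacement. The permitted CFU range of the capsule (Protocol 9.1) is a product specification, not evidence of spread in stool.

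Finally, the 15% rule covers on-treatment values only. Baselines may be largely undetectable, and a fold change then leans on the substitute value. This is a real cost of the log scale and the reason to keep the raw median beside it.

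**Conclusion.** The point holds as a minor one. The visible text summarises stool counts on the untransformed scale and states no log10 scale, geometric mean or ratio. If the log10 SD is 0.75 to 1.5, one subject typically supplies 49% to 74% of the group total at 8 per group and 58% to 81% at 5. The mean, SE and mean change can then be dominated by that subject, while the planned median, quartiles and listings limit the damage without removing it. The size rests on an assumed log-normal spread, on roughly balanced groups, and on the addendum not already setting the scale.

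The association endpoint has no method or listed output in the SAP. That gap does not depend on the assumed spread.

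A reader might go further and claim lost power to detect a group difference. The documents do not support this. The O-O and P-O groups are set side by side descriptively, no interval or test is planned for stool, and both groups receive Oxabact at month 24. This is a supportive endpoint, and no primary or key secondary conclusion changes.

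**What to change.** 1. In SAP 7.6.3 (Stool), derive log10(count per gram) after detection-limit substitution, separately by genotype. Report the geometric mean and the geometric mean fold change from each applicable baseline, with a 95% confidence interval labelled descriptive.
2. Keep the planned raw median, quartiles and range in the same table, and give the number of subjects with an undetectable baseline.
3. Footnote the substitute value and say how far the fold change depends on it, for instance by repeating it with half that value.
4. Add to SAP 12.3 a figure of log10 change in count against change in total plasma oxalate, with subjects marked by group and undetectable baselines flagged.
5. If the addendum already sets a log scale, state it in SAP 7.6.3.

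The cost is one derived variable, a few table rows and one figure. The drawback is the dependence on the substitute value, which items 2 and 3 make visible. The scale should be fixed before the stool data are reviewed.

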6.3.3 Post-treatment follow-up

Previous clinical experience with Oxabact suggests that the bacteria only transiently colonise the gastrointestinal tract and fecal recovery generally drops below detectable levels one to two weeks after end of study treatment (Hoppe et al. 2006).

A post-treatment safety follow-up will cover a duration of 4 weeks after the last dose of study treatment. The follow-up will be performed as a telephone call maximum three working days after the end of the safety follow-up period. The subject will be asked for any AEs (incl. kidney stone events) appearing after end of last dose of study treament. Additionally, any AEs that were present at the last completed study visit should be followed-up. Concomitant medication taken during the safety follow-up period should also be recorded.

Adverse Drug Reactions, which are unresolved at the time of safety follow-up call, should be followed by the Investigator until the event has resolved or, if persistent, has been assessed as chronic or stable.

Subjects will provide a post-treatment follow-up stool sample 4 weeks (plus maximum 3 working days) after intake of last dose of study drug.

End of study is defined as when the safety follow-up telephone-call and the post-treatment stool sample have been completed.

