12.7 Other Endpoints

- Change from baseline in myocardial function parameters as measured by Speckle Tracking and traditional echocardiography) will be summarised descriptively over time after 12 and 24 months of open-label Oxabact treatment.

 STE results will be evaluated over time for global longitudinal strain, including segmental changes, short-axis myocardial function, rotational displacement and apical sparing patterns. Traditional echocardiographic parameters will also be evaluated over time (e.g. Ejection Fraction, End Diastolic Volume, e/é, e/a, Left Ventricular End Diastolic Dimension, Fractional shortening, Tricuspid Regurgitation by Doppler as an indicator of right ventricular/pulmonary pressure.). A positive treatment effect would be an improved myocardial function based on the above-mentioned parameters, decreased global longitudinal strain, improved rotational displacement and reduced/removed apical sparing pattern. Change from baseline in free plasma oxalate after 12 and 24 months of open-label Oxabact treatment will be described similar to the primary endpoint.
- Change from baseline in urinary oxalate excretion after 12 and 24 months of open-label Oxabact treatment will be described.
- Grade of nephrocalcinosis after 12 and 24 months of open-label Oxabact treatment will be summarised. Grade of nephrocalcinosis will be assessed by ultrasound images using grades 0-3.
- Number of *O. formigenes* during the study will be summarised over time. Summaries will present both observed and change from baseline values overall and by genotype (genotype 1, and genotype 2). In the P O group, change from second baseline will be used instead. The association between *O. formigenes* in

- stool and total plasma oxalate concentration will be evaluated using graphical displays.
- Change from baseline in Quality of Life scores as measured by SF36V2 or CHQ/PF50 questionnaires, depending on age, will be summarised over time in the two treatment groups.
- Change from baseline after 12 and 24 months of open-label Oxabact treatment in markers for renal function, renal tubular capacity and inflammation in urine and plasma will be described. Remaining time-points during the study will be presented as supportive.

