2.3 Study medication

Subjects will receive open label OC5 (Oxabact) twice daily for 24 months.

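### The stool endpoint rests on O-O versus P-O at month 24, when both groups take Oxabact, so the named comparison cannot show whether the drug raises O. formigenes counts

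*SAP*

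**What the plan says.** SAP 7.6.3 (Stool) first plans descriptive statistics of observed values and changes "per treatment group and overall over time, using two baselines". It then names the basis of the endpoint: the count "at month 24 compared to baseline in the O - O group versus the P - O group". It adds: "The measurement at month 12 will be used as supportive data". On treatment, SAP 2.3 states: "Subjects will receive open label OC5 (Oxabact) twice daily for 24 months".

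SAP 7.1 defines the second baseline as the last planned value before open-label drug, applies it to P-O only and calls it supportive. It lists faeces among the parameters for which both baselines are used, and puts pooled ePHex data into the efficacy summaries.

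The protocol frames the endpoint differently:
- Section 12.7 plans stool summaries over time, overall and by genotype. It says: "In the P O group, change from second baseline will be used instead". It names no key month and no comparison between O-O and P-O.
- Section 10.6.1 says that a positive treatment effect "should show an increased number of *O. formigenes* genotype 1 during treatment period".
- Section 6.3.3 reports that previous experience suggests that "the bacteria only transiently colonise the gastrointestinal tract and fecal recovery generally drops below detectable levels one to two weeks" after treatment ends.

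SAP section 8, which lists changes from the protocol, does not mention stool.

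**The concern.** Protocol 10.6.1 asks an on-drug versus off-drug question: does genotype 1 rise under treatment? The comparison named in the SAP sets two dosed groups against each other. What separates them is how long they have been dosed: 36 versus 24 months of Oxabact at month 24, and 24 versus 12 months at month 12.

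The protocol calls stool monitoring an important tool for following the drug's pharmacodynamics. If the result named as the basis of the endpoint shows no group difference, a reader of the study report may conclude that the product did not raise counts, when it may have raised them equally in both groups.

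**Working it through.** Neither document gives a planning figure for stool. The only power calculation, Protocol Table 11, is for eGFR and does not bear on this point.

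**Inputs**
- Stool is scheduled at months 0, 6, 12, 18 and 24 (Protocol Table 5). Month 0 is normally ePHex week 52, when O-O is on Oxabact and P-O on placebo.
- Write b for the count at ePHex baseline, E for the on-drug rise, D for any additional rise from O-O's extra year of dosing, and δ for any drift in P-O during the placebo year. None of these values is in the documents.

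**Month 24, ePHex baseline in both groups**
- O-O change: (b + E + D) − b = E + D
- P-O change: (b + E) − b = E
- Difference: D

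**Month 24, second baseline for P-O**
- O-O change: E + D
- P-O change: (b + E) − (b + δ) = E − δ
- Difference: D + δ

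E drops out both times. With no duration effect and no drift the expected difference is zero. The same algebra applies at month 12.

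**Comparisons that keep E**
- ePHex week 52, O-O versus P-O change from ePHex baseline: E − δ
- Within P-O, any month from 6 to 24 minus second baseline: E − δ

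**Illustration.** Mean estimates from 20,000 simulated trials with 8 per group. Assumed: SD 1 log10, correlation 0.5 between samples, D = 0 and δ = 0.

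| Assumed rise E (log10) | Month 24, ePHex baseline | Month 24, second baseline for P-O | Week 52, O-O versus P-O | Within P-O, month 24 minus second baseline |
|---|---|---|---|---|
| 0 | −0.003 | 0.001 | −0.004 | −0.004 |
| 1 | −0.004 | −0.002 | 0.995 | 1.000 |
| 2 | 0.003 | 0.002 | 2.006 | 2.001 |
| 4 | −0.001 | 0.001 | 3.996 | 4.001 |

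With an assumed duration effect D of 0.5 log10 and E = 2, the two month-24 columns give 0.498 and 0.497. They recover D and nothing of E.

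**Numbers available.** Month 24 is also the scheduled time with fewest subjects. At the planned 25% drop-out per year, 16 × 0.75 × 0.75 = 9 remain (SAP 2.4). The 18 subjects actually included would give 18 × 0.75 × 0.75 ≈ 10.

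**The case against.** The strongest reply is that the SAP already presents what is needed. The sentence before the one at issue plans summaries over time with two baselines, and ePHex data are pooled in. The P-O change from second baseline is therefore planned, and week-52 counts by group should be available. This stands, and it limits the point to which comparison is named as the basis. A reader might infer that the trial cannot show colonisation at all; the documents do not support that.

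Other tempting readings also go too far:
- **That the placebo phase plays no part.** The month-24 sentence does not say which baseline it uses. With the second baseline, P-O's reference is normally the end-of-placebo value. The group difference still loses E.
- **That the output would be the same whether or not the drug colonises.** SAP 7.6.3 runs the stool analyses only if less than 15% of on-treatment values are below the limit of detection. Without colonisation that condition would probably fail, leaving a listing.
- **That transience is established.** Protocol 6.3.3 says only that experience suggests it, and it concerns stopping. It does not show that 36 and 24 months of dosing give equal counts. Genotype 2, which rose under OC5 in earlier studies (Protocol 10.6.1), might depend on duration, so the month-24 comparison has some descriptive use.
- **That this is a loss of power.** SAP 7.1 excludes formal testing, and no effect size or SD for stool is given. A power figure would describe no planned analysis.

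The point also depends on the SAP 7.1 options. Under option 2 no stool summary is produced. Option 3 starts with an agreed selection of outputs and then leads to option 1 or 2.

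**Conclusion.** The point holds, at minor severity. The comparison that SAP 7.6.3 names as the basis of the stool endpoint has an expected value that does not depend on the on-drug rise, with either P-O baseline. At most it shows an effect of an extra year of dosing, or placebo-year drift if the second baseline is used. A working product would be expected to read as no group difference.

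The SAP also gives the second baseline a supportive role, where Protocol 12.7 uses it in place of the ePHex baseline for P-O, and adds a group comparison that the protocol does not contain. Neither change is recorded in SAP section 8, so the two texts need reconciling in any case.

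The harm is to interpretation only: this is an 'other' endpoint, summarised descriptively, and the informative summaries are planned alongside it. The conclusion assumes that both groups take the same product at months 12 and 24, as SAP 2.3 states, and that drift under placebo is small.

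**What to change.** In SAP 7.6.3 (Stool), replace the month-24 sentence and the month-12 sentence with the following:

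1. **Main stool result:** the within-subject change in P-O from second baseline to months 6, 12, 18 and 24, in line with Protocol 12.7.
2. **Added comparison:** O-O versus P-O change from ePHex baseline at ePHex week 52. Use the on-treatment week-52 sample, not a new visit 0 taken after a delayed transfer. Label it as a descriptive comparison in the subset that entered the extension.
3. **Persistence:** counts by group at months 12 and 24, described as persistence on long-term dosing, with the baseline stated for each change.

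Record the change in SAP section 8.

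The cost is SAP wording and an extra row or column in Table 14.2.47. The samples are already scheduled, and ePHex data are integrated under option 1. There are two drawbacks. The week-52 comparison partly repeats the ePHex result in a selected subset: 18 subjects were included (SAP 2.4), against 25 randomised in ePHex by June 2020 (Protocol 4.4.1.8). The P-O change is a before-after comparison with no concurrent control, which is why the week-52 comparison should stand beside it.
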